Results from a PK study of cabozantinib in subjects with renal impairment indicated that the ratios of geometric least squares (LS) mean for maximum plasma concentration (Cmax) and AUCs (AUC from 0 h to the last sampling time point [AUC0-t] and AUC from 0 h to infinity [AUC0-inf]) were 19% and 30% higher, respectively, for subjects with mild renal impairment compared to subjects with normal renal function. For subjects with moderate renal impairment, both Cmax and AUCs appeared to be similar when compared with subjects with normal renal function (differences: < 3% and < 7%, respectively). Results from a PK evaluation of cabozantinib in subjects with hepatic impairment indicated that exposure (AUC0-inf) to cabozantinib was increased by about 81% and 63% in subjects with mild and moderate hepatic impairment, respectively. There are no PK data in subjects with severe renal or hepatic impairment.

A high-fat meal increased Cmax and AUC values by 41% and 57%, respectively, relative to fasted conditions in healthy subjects administered a single 140-mg oral cabozantinib capsule dose.

Cabozantinib is a substrate of cytochrome P450 (CYP)3A4 in vitro. Inhibition of CYP3A4 reduced the formation of the cabozantinib N-oxide metabolite by > 80%. Inhibition of CYP2C9 had a minimal effect on cabozantinib N-oxide metabolite formation (ie, a < 20% reduction). Inhibition of CYP1A2, CYP2A6, CYP2B6, CYP2C8, CYP2C19, CYP2D6 and CYP2E1 had no effect on cabozantinib N-oxide metabolite formation. In healthy subjects, cabozantinib plasma AUC0-inf was increased 38% with coadministration of the strong CYP3A4 inhibitor ketoconazole and decreased 77% with coadministration of the strong CYP3A4 inducer rifampin (rifampicin).

Cabozantinib is a noncompetitive inhibitor of CYP2C8 (Kiapp = 4.6 μ M), a mixed-type inhibitor of both CYP2C9 (Kiapp = 10.4 μ M) and CYP2C19 (Kiapp = 28.8 μ M), and a weak competitive inhibitor of CYP3A4 (estimated Kiapp = 282 μ M) in human liver microsome (HLM) preparations. Concentration associated with 50% inhibition (IC50) values > 20 μ M were observed for CYP1A2, CYP2D6, and CYP3A4 isozymes in both recombinant and HLM assay systems. Cabozantinib at steady-state plasma concentrations (\geq 100 mg/day daily dosing for a minimum of 21 days) showed no effect on single-dose rosiglitazone (a CYP2C8 substrate) plasma exposure (Cmax and AUC) in subjects with solid tumors.

Cabozantinib is an inducer of CYP1A1 mRNA in human hepatocyte incubations (ie, 75-100% of CYP1A1 positive control β -naphthoflavone induction) but not of CYP1A2, CYP2B6, CYP2C8, CYP2C9, CYP2C19 or CYP3A4 mRNA or isozyme-associated enzyme activities.

Concomitant administration of proton pump inhibitor (PPI) esomeprazole resulted in no clinically relevant effect on cabozantinib plasma PK in healthy subjects.

Cabozantinib is an inhibitor (IC50 = 7.0 μ M), but not a substrate, of P-glycoprotein (P-gp) transport activities in a bi-directional assay system using MDCK-MDR1 cells. In addition, cabozantinib was shown to be a substrate of

drug transporter multidrug resistance-associated protein 2 (MRP2) in an in vitro assay.

1.6 Nivolumab and ipilimumab – further information

Nivolumab (BMS-936558, MDX-1106, and ONO-4538) is a fully human monoclonal immunoglobulin G4 (IgG4) antibody (HuMAb) that is specific for human programmed death-1 (PD-1, cluster of differentiation 279 [CD279]) cell surface membrane receptor (Investigator Brochure, 2016). PD-1 is a negative regulatory molecule that is expressed transiently following T-cell activation and on chronically stimulated T cells characterized by an “exhausted” phenotype. Nivolumab binds to cynomolgus monkey PD-1 but not mouse, rat, or rabbit molecules. Clinical activity of nivolumab has been observed in patients with melanoma, non-small cell lung cancer (NSCLC), and renal cell carcinoma (RCC). The combination of nivolumab and ipilimumab (anti-cytotoxic T lymphocyte associated antigen-4 [anti-CTLA-4]) in a phase 1/2 trial showed markedly enhanced clinical activity with an acceptable safety profile in melanoma patients (Wolchok et al., 2013).

The clinical use of monoclonal antibodies to T-cell inhibitory receptors has provided transformative information on the nature of the immune system and cancer. An emerging picture suggests that endogenous immune responses can mediate effective tumor regression and/or improved survival even in patients with large volume tumors resistant to other forms of therapy. Some of the unique features of this type of therapy, based largely on experience in advanced melanoma, include: improved overall survival (OS) with or without radiographic responses or improved progression-free survival (PFS); responses that may be delayed or occur after radiographic disease progression; combinations of immune modulators with enhanced or novel activities (in the example of ipilimumab and nivolumab); and toxicity that is almost exclusively immune or inflammatory in nature. It is not yet clear what factors determine responses and which components of the immune system are needed for this to occur. It seems likely that both memory helper and effector cells would be needed to sustain long-term responses. Increasing emphasis has been placed on understanding the relationships of the tumor, cellular infiltrate, and immunologic milieu surrounding each tumor.

PD-1, a 55-kDa type 1 transmembrane protein, is a member of the CD28 family of T-cell co-stimulatory receptors that include Ig super family member CD28, CTLA-4, inducible co-stimulator (ICOS), and B and T lymphocyte attenuator (BTLA) (Investigator Brochure, 2016). PD-1 is transiently but highly expressed on activated T cells functioning to limit immune effectors at the site of activation. Chronic stimulation may prevent the re-methylation of the PD-1 gene leading to continuous expression and characterizes a state of “exhausted” T cells that lose function and proliferative capacity while enhancing a suppressive tumor microenvironment. PD-1 may act together with other T-cell modulating molecules, including CTLA-4, TIM-3, lymphocyte-activation gene 3 (LAG-3) as well as indoleamine-pyrrole 2,3-dioxygenase 1 (IDO-1), cytokines, and transforming growth factor beta (TGF-beta).

Two ligands specific for PD-1 have been identified: PD-ligand 1 (PD-L1, also known as B7-H1 or CD274, expressed on tumor, antigen-presenting cells [APCs], and dendritic cells [DCs]) and PD-L2 (also known as B7-DC or CD273, expressed on endothelial cells). The interaction of PD-1 with PD-L1 and PD-L2

results in negative regulatory stimuli that down-modulate the activated T-cell immune response through SHP-1 phosphatase.

PD-1 knockout mice develop strain-specific lupus-like glomerulonephritis (C57BL/6) and cardiomyopathy (BALB/c). In transplantable tumor models that expressed PD-1 and LAG-3 on tumor-infiltrating CD4+ and CD8+ T cells dual anti-LAG-3/anti-PD-1 antibody treatment cured most mice of established tumors that were largely resistant to single antibody treatment (Woo et al., 2012). Despite minimal immunopathologic sequelae in PD-1 and LAG-3 single knockout mice, dual knockout mice abrogated self-tolerance with resultant autoimmune infiltrates in multiple organs, leading to eventual lethality.

PD-L1 expression is found on a number of tumors, and is associated with poor prognoses based on OS in many tumors, including melanoma (Taube et al., 2012), renal (Thompson et al., 2004; Thompson et al., 2005; Thompson et al., 2006), esophageal (Ohigashi, et al. 2005), gastric (Wu et al., 2006), ovarian (Dong et al., 2003), pancreatic (Nomi, et al., 2007), lung (Zitvogel, et al., 2006), and other cancers (Investigator Brochure, 2016).

The PD-1/PD-L1 axis plays a role in human infections, particularly in hepatitis C virus (HCV) and human immunodeficiency virus (HIV). In these cases, high expression levels of PD-1 were found in viral-specific CD8+ T cells that also display a non-responsive or exhausted phenotype. Non-responsive PD-1-high T cells were observed in simian immunodeficiency virus (SIV) infection in rhesus macaques. Treatment of SIV-infected macaques with an anti-PD-1 mAb (3 mg/kg x4) resulted in decreased viral loads and increased survival along with expanded T cells with increased T-cell functionality.

Nonclinical Development of Nivolumab

In intravenous (IV) repeat-dose toxicology studies in cynomolgus monkeys, nivolumab alone was well tolerated (Investigator Brochure, 2016). Combination studies have highlighted the potential for toxicity when combined with ipilimumab, MDX-1408, and BMS-986016. Nivolumab bound specifically to PD-1 (and not to related members of the CD28 family such as CD28, ICOS, CTLA-4, and BTLA) with a $K_d = 3.06$ nM. A surrogate rat anti-mouse PD-1 antibody (4H2) was derived and expressed as chimeric IgG1 murine antibody. Antitumor activity was seen for several tumor models, including colon carcinoma and fibrosarcoma.

Clinical Development of Nivolumab

Nivolumab is being evaluated as monotherapy and in combination with cytotoxic chemotherapy, other immunotherapy (such as ipilimumab), anti-angiogenesis therapy, and targeted therapies in completed and ongoing BMS-sponsored clinical trials in NSCLC, melanoma, RCC, hepatocellular carcinoma (HCC), gastrointestinal (GI) malignancies including microsatellite instability (MSI) in colorectal cancer, and triple-negative breast cancer (TNBC) with an expanding group of indications (Investigator Brochure, 2016). In addition, two investigator-sponsored trials (ISTS) of nivolumab in combination with a peptide vaccine in melanoma are being conducted in the adjuvant setting and advanced disease.

Seven nivolumab studies were conducted in Japan, including six studies in advanced solid tumors and recurrent or unresectable stage III/IV melanoma sponsored by Ono Pharmaceuticals Co. Ltd., and one IST in recurrent or advanced platinum-refractory ovarian cancer.

Pharmacokinetics

Pharmacokinetics (PK) of nivolumab was linear in the range of 0.3 to 10 mg/kg, with dose-proportional increases in maximum serum concentration (Cmax) and area under the concentration-time curve from time zero to infinity (AUC_{0-∞}), with low to moderate inter-subject variability observed at each dose level (Investigator Brochure, 2016). Clearance of nivolumab is independent of dose in the dose range (0.1 to 10 mg/kg) and tumor types studied. Body weight normalized dosing showed approximately constant trough concentrations over a wide range of body weights. The mean terminal elimination half-life of BMS-936558 is 17 to 25 days consistent with the half-life of endogenous IgG4.

Efficacy

In a phase 1 (1, 3, and 10 mg/kg nivolumab doses) dose-escalation study the 3 mg/kg dose was chosen for expanded cohorts. Among 236 patients, objective responses (ORs) (complete or partial responses [CR or PR]) were seen in NSCLC, melanoma, and RCC. ORs were observed at all doses (Sznol et al., 2013). Median OS was 16.8 months across doses and 20.3 months at the 3 mg/kg dose. Median OS across all dose cohorts was 9.2 months and 9.6 months for squamous and non-squamous NSCLC, respectively (Brahmer et al., 2013). In the RCC cohort, median duration of response was 12.9 months for both doses with 5 of the 10 responses lasting ≥1 year (Drake et al., 2013).

In an advanced melanoma phase 1 study, nivolumab and ipilimumab were administered IV every 3 weeks for 4 doses followed by nivolumab alone every 3 weeks for 4 doses (concurrent regimen) (Wolchok et al., 2013). The combined treatment was subsequently administered every 12 weeks for up to 8 doses. In a sequenced regimen, patients previously treated with ipilimumab received nivolumab every 2 weeks for up to 48 doses. In the concurrent regimen (53 patients), 53% of patients had an OR at doses 1 mg/kg nivolumab and 3 mg/kg ipilimumab, with tumor reduction of 80% or more (modified World Health Organization [mWHO] criteria). In the sequenced-regimen (33 patients), the objective response rate (ORR) was 20%.

In a phase 1 study of nivolumab plus platinum-based doublet chemotherapy (PT-doublet) in chemotherapy-naïve NSCLC patients, 43 patients were treated with nivolumab + PT-doublet (Rizvi et al., 2013). No dose-limiting toxicities (DLTs) were reported and total/confirmed ORRs were 43/33%, 40/33%, and 31/31% in nivolumab/gemcitabine/cisplatin, nivolumab/pemetrexed/cisplatin, and nivolumab/carboplatin/paclitaxel arms, respectively.

Toxicology

A maximum tolerated dose (MTD) of nivolumab was not defined (Topalian et al., 2012). Serious adverse events (SAEs) occurred in 32 of 296 patients (11%) similar to the immune-related inflammatory events seen with ipilimumab: pneumonitis, vitiligo, colitis, hepatitis, hypophysitis, and thyroiditis (with noted pulmonary toxicity resulting in 3 deaths). Renal failure, symptomatic pancreatic and DM, neurologic events, and vasculitis have also been reported.). In combination with ipilimumab in the concurrent-regimen group (Wolchok et al., 2013), grade 3 or 4 treatment-related events were noted in 53% of patients. Skin rash represents the majority of these events.

Pharmacodynamics/Biomarkers

Tumor-cell expression (melanoma) of PD-L1 was characterized in combination with ipilimumab with the use of IHC staining and pharmacodynamics changes in the peripheral-blood absolute lymphocyte count (Wolchok et al., 2013). With PD-L1 positivity defined as expression in at least 5% of tumor cells, biopsy specimens from 21 of 56 patients (38%) were PD-L1-positive. Among patients treated with the concurrent regimen of nivolumab and ipilimumab, ORs were observed in patients with either PD-L1-positive tumor samples (6 of 13 patients) or PD-L1-negative tumor samples (9 of 22). In the sequenced regimen cohorts, a higher number of overall responses was seen among patients with PD-L1-positive tumor samples (4 of 8 patients) than among patients with PD-L1-negative tumor samples (1 of 13) suggesting the possibility that these tumors have higher response rates to the combination. The relationship between PDL-1 expression and responses may not be present in patients treated with the combination. Tissue expression of PDL-2, interferon- γ (IFN- γ), IDO, and T cell CD8+ are of current interest. Until more reliable data based on standardized procedures for tissue collection and assays are available, PD-L1 status cannot be used to select patients for treatment at this time.

Ipilimumab (BMS-734016, MDX010, MDX-CTLA4, YervoyTM) is a fully human monoclonal immunoglobulin (Ig) G1k specific for human cytotoxic T lymphocyte antigen 4 (CTLA-4, CD152), which is expressed on a subset of activated T cells (Ipilimumab Investigator Brochure, 2017). CTLA-4 is a negative regulator of T-cell activation. Ipilimumab binds to CTLA-4 and inhibits its interaction with ligands on antigen-presenting cells (APCs). The proposed mechanism of action for ipilimumab's effects in subjects with melanoma is indirect, possibly through T-cell potentiation and mediation of antitumor immune responses.

Ipilimumab has been approved for the treatment of unresectable metastatic melanoma in over 40 countries including the United States (US, March 2011), the European Union (July 2011), and Australia (July 2011).

BMS and Medarex (acquired by BMS in Sep-2009) have co-sponsored an extensive clinical development program for ipilimumab, encompassing > 13,800 subjects in several cancer types in completed and ongoing studies, including a compassionate use program (Ipilimumab Investigator Brochure, 2017). The focus of the clinical program is in melanoma, prostate cancer, and lung cancer, with advanced melanoma being the most comprehensively studied indication. Ipilimumab is being investigated both as monotherapy and in combination with other modalities such as chemotherapy, radiation therapy, and other immunotherapies.

CTEP's clinical development of ipilimumab focuses on cervical, gastrointestinal, ovarian, prostate cancer, chronic lymphocytic leukemia, head and neck squamous cell carcinoma, solid tumors, Hodgkin and non-Hodgkin lymphomas, melanoma, and myelodysplastic syndrome.

While the toxicity and clinical responses overlap, mechanisms of immune activation and range of responses appear to be different for each of the single agents.

Preclinical data support the combinations of nivolumab and ipilimumab (Curran et al., 2010).

The combination of ipilimumab with nivolumab has been reported to result in improved responses in advanced melanoma marked by time to response, number of responses, depth and duration of responses, PFS, and OS compared to single agent ipilimumab (Wolchok et al., 2013).

For RCC results have been reported (Hammers et al., 2014).

The combination is being evaluated in other disease settings typically with 3mg/kg nivolumab and 1mg/kg ipilimumab q 3 weeks x 4 induction doses.

The rationale for the doses selected in this trial is outline in Section [1.2](#), above.

1.7 Imaging of therapy response to immune checkpoint inhibition

Therapy with immune checkpoint inhibitors can lead to unconventional tumor responses resulting from immune activation [90,91,92]. Radiologic pseudoprogression describes an unconventional imaging pattern of tumor response where tumors initially exhibit features of progression, including tumor enlargement and/or development of new lesions, with subsequent radiologic tumor response evident on serial imaging with sustained therapy [90]. Several new imaging response criteria have been proposed for measurement of tumor response in solid tumors undergoing immune checkpoint inhibitor therapy including the immune related response criteria (irRC) [90], an adaption of the irRC termed the uni-dimensional irRC [93] and, most recently, the iRECIST criteria [94]. These immune criteria have been put forth with the goal of more accurately classifying unconventional tumor responses as non-progression. However, it is yet unclear if any of these new criteria present a benefit over the conventional Response Evaluation in Solid Tumor (RECIST) 1.1 [95] for use as an imaging endpoint in clinical trials of immune checkpoint inhibition in solid tumors. Here we propose an explorative correlative imaging aim to define tumor response assessed by RECIST1.1, unidimensional irRC and iRECIST, assessed by central review. The hypothesis for this imaging aim will be that significant differences exist in the calculation of best overall response and progression-free survival amount the examined tumor response criteria. Interpretation of the response data will be performed noting the bias in the availability patient imaging for analysis with immune criteria since only patients maintained on therapy beyond imaging evidence of progression (ie. clinically suspected of radiologic pseudoprogression) will have the required imaging data (subsequent re-imaging to confirm suspected progression). While this is a limitation to the interpretation to the immune criteria imaging response data, the data obtained is felt to be valuable in better understanding the application of these imaging criteria to clinical trials of immunotherapeutics.

Finally, this clinical trial utilizes a study site calculation of RECIST1.1 response for patients enrolled in this study. Typically these measurements are calculated by study personnel that are trained in RECIST1.1 measurement but are not radiologists. This strategy is employed in many clinical trials that do not include a central reading of imaging response. Here we will compare the RECIST1.1 calculations determined at the study sites to those generated by central review to determine if there are significant differences in the measurements obtained between these two imaging assessment approaches. The hypothesis will be that no significant difference exists between measurements of RECIST1.1 between study imaging site and central review.

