2.4 Imaging Endpoints

- 2.4.1 To describe time point tumor response assessment, overall best response and progression-free survival using the conventional RECIST1.1 criteria and the exploratory uni-dimensional immune response criteria (iRRC) and the iRECIST criteria with all measurements performed by the central review.
- 2.4.2 To compare RECIST1.1 imaging response assessment measurements (time point response assessment and overall best response) assess by site study personnel to those performed by central review.

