6.1.4.7 Duration of Response

Duration of Overall Response

The duration of overall response is measured from the time measurement criteria are met for CR or PR (whichever is first recorded) until the first date that recurrent or progressive disease is objectively documented (taking as reference for progressive disease the smallest measurements recorded since the treatment started).

The duration of overall CR is measured from the time measurement criteria are first met for CR until the first date that progressive disease is objectively documented.

Duration of Stable Disease

Stable disease is measured from the start of the treatment until the criteria for progression are met, taking as reference the smallest measurements recorded since the treatment started, including the baseline measurements. To be assigned a status of stable disease, measurements must have met the stable disease criteria at least once after entry to that step at a minimum interval 7 weeks.

6.2 Exploratory imaging correlates:

Imaging correlates performed for this study will be performed using the baseline study and 1st 3 follow-up time points, when available. All CT and FDG-PET/CT imaging data obtained for patients participating in this clinical trial at baseline and through the first 3 follow-up imaging time points will be de-identified and uploaded from the study site into Transmission of Imaging and Data (TRIAD®) database and delivered to the ACR Imaging Core Laboratory within 48 hrs. of completion. Using this submitted imaging data, the following measurements will be performed.

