6.2.1 RECIST1.1 (central review)

Measurements of RECIST1.1 response will be performed as described in Section [6.1](#) with time point and overall best response assessments categorized as complete response (CR), partial response (PR), stable disease (SD), or progressive disease (PD). These measurements will be performed by the central review and will only be used for analyses for the exploratory imaging correlates.

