9.3 Statistical Analysis Plan

The primary and some secondary analyses will include all eligible and treated patients. Exceptions to this include: analysis of toxicity data, which will include all patients who received study drug regardless of eligibility, and analyses of response, which will include eligible and treated patients with measurable and evaluable disease.

Time-to-event data, such as PFS and OS, will be estimated using the Kaplan-Meier method, and Cox proportional hazards models will be used to estimate the treatment hazard ratios. The primary comparison of PFS will use a logrank test stratified on the randomization stratification factors with a one-sided type I error rate of 10%. Other comparisons of groups will be made using the logrank test and Cox modeling.

Categorical data, such as response rates (CR+PR) and toxicity, will be compared using Fisher's exact tests with a one-sided type I error rate of 10%; multivariable logistic regression modeling will be used to adjust for the effect of any covariates that are associated with these categorical outcomes. Though none are currently planned, any continuous outcomes will be analyzed using Wilcoxon rank sum test, and multivariable linear regression models may be used to adjust for multiple associations with outcome.

Modeling procedures will implement backward selection; variables significant at the 0.10 level in the univariate setting will be chosen for inclusion in an initial full model, and at each step the least significant variable will be removed from the model. Only those covariates with $p < 0.05$ will remain in any final models, unless there are factors identified by the study team as crucial to model interpretation.

Point estimates of all endpoints will be accompanied by the corresponding two-sided 80% confidence intervals.

In the event that there are missing data, no imputation of the missing data will be conducted. We will assume that data are missing at random and will conduct all analyses as originally planned because we do not anticipate an excess of missing data.

Subset analyses are planned for all stratification factors and all known prognostic factors, such as performance status, age, sites of metastases, gender, etc. Subset analyses of all variables, including correlatives, are considered to be exploratory in nature.

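### The exploratory site-versus-central RECIST 1.1 comparison is framed as a search for a significant difference, and a non-significant result would not show that the reads agree

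*Combined protocol and SAP*

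**What the plan says.** Section 1.7 explains that site RECIST 1.1 results usually come from trained study staff who are not radiologists. It plans to compare them with central review in order to "determine if there are significant differences in the measurements obtained between these two imaging assessment approaches". It then gives the expected result: "The hypothesis will be that no significant difference exists between measurements of RECIST1.1 between study imaging site and central review".

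Objective 2.4.2 is the operative statement and says only: "To compare RECIST1.1 imaging response assessment measurements (time point response assessment and overall best response) assess by site study personnel", against the central reads. Section 6.2.1 classes each central read as CR, PR, SD or PD, and says that these reads "will only be used for analyses for the exploratory imaging correlates". On the material available, Section 6.2 says: "Imaging correlates performed for this study will be performed using the baseline study and 1st 3 follow-up time points, when available".

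Section 9.2 defines PFS, overall survival and best response for the imaging study but describes no site-versus-central analysis. Section 9.3 names no method for this comparison either. Its general rule is that categorical data "will be compared using Fisher's exact tests with a one-sided type I error rate of 10" percent, which is a test for independent groups. It also attaches two-sided 80% confidence intervals to point estimates of all endpoints, but no agreement measure is listed as an endpoint. The documents contain no kappa, percent agreement, limits of agreement, intraclass correlation or equivalence margin for this comparison.

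**The concern.** The question is whether two readers give the same patient the same classification. A difference test asks whether one reader's results are shifted as a whole against the other's. If the site calls 15% of patients responders whom the central reader does not, and the central reader does the same for another 15%, the totals match and the test sees nothing, although 30% of patients are classified differently.

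Because the hypothesis is itself the absence of a significant difference, failure to reject is the expected result and reads naturally as confirmation. With no margin, this is not an equivalence design. At stake is the inference about site reads: Section 9.2 bases PFS on site review, and Section 1.7 notes that many trials have no central reading, so a report of no significant difference could be cited as validation of site measurement.

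**Working it through.** **Plan's own figure.** None exists for this comparison: no sample size, level, margin or target. The patient numbers come from Section 9.4: 129 eligible and treated; 129/0.9 = 143.3, rounded up to 144 randomized; 144 + 25 in Arm T = 169. The number of paired reads is not stated.

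**Assumptions, not in the documents.** One binary response (CR+PR or not) per patient, n = 129, 20% response by each reader, discordance *d* split equally, exact McNemar test.

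**Step 1: agreement.** At *d* = 30% the four cells are: both respond 0.05, site only 0.15, central only 0.15, neither 0.65. Observed agreement is 0.05 + 0.65 = 0.70. Chance agreement is 0.20² + 0.80² = 0.68. Kappa = (0.70 − 0.68)/(1 − 0.68) = 0.02/0.32 = 0.06. At *d* = 10%, kappa = (0.90 − 0.68)/0.32 = 0.69.

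**Step 2: probability of a significant result.** The discordant count D is Binomial(129, *d*). Given D, the site-only count is Binomial(D, ½). Summing the exact rejection probability over D gives:

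| Discordance | Kappa | Significant, two-sided 5% | Significant, one-sided 10% |
|---|---|---|---|
| 10% | 0.69 | 2.5% | 5.9% |
| 20% | 0.38 | 3.0% | 6.9% |
| 30% | 0.06 | 3.4% | 7.6% |

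At 30% discordance the test is non-significant in 100 − 3.4 = 96.6% of trials at two-sided 5%, and in 100 − 7.6 = 92.4% at one-sided 10%. The result barely moves while kappa falls from 0.69 to 0.06.

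**Step 3: a net shift.** Split the same 30% discordance 20/10 instead of 15/15, so that the site-only count is Binomial(D, 2/3). The test is now significant in 49% of trials at two-sided 5% and in 75% at one-sided 10% in that direction.

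**Step 4: other tests.** Two readers were simulated as classifying independently into CR/PR/SD/PD with equal shares (assumed 2/18/35/45% or 2/28/35/35%; N = 50, 129, 144, 169). Kappa averages about 0 and raw agreement is 32–36%. Stuart-Maxwell, Bowker, exact McNemar at 5% and 10%, and one-sided 10% Fisher tests were non-significant in 92–98% of trials. A paired t-test on uncorrelated measurements was non-significant in 94–95%. At N = 129, Stuart-Maxwell was non-significant in 95%, 96% and 98% of trials at kappa 0, 0.4 and 0.8.

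**Step 5: limits and the converse.** With independent readers and unequal response rates at N = 129, McNemar at 5% was non-significant in 87% of trials for 20% versus 25%, 59% for 20% versus 30%, and 8% for 20% versus 40%. Conversely, continuous readings correlated at about 0.99 with a systematic shift of 2 units (between-patient SD 30, difference SD 5) were declared different in more than 99% of trials.

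**Step 6: what estimation would give.** With shares 2/18/35/45%, one response per patient and true kappa 0.6 to 0.8, the simulated standard error of kappa is 0.061 to 0.046 at N = 129. The 80% half-width is 1.282 × 0.061 = 0.08 down to 1.282 × 0.046 = 0.06. At N = 50 the standard errors are 0.096 to 0.076, giving 0.12 to 0.10.

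**The case against.** The strongest reply is that the plan does not commit itself to the inference. Section 1.7 is background, objective 2.4.2 only says to compare, and Section 9 contains no decision rule. A reader might infer that the plan will declare site reads equivalent to central reads, but the documents stop short of that. What stands is narrower: the only stated hypothesis is the absence of a significant difference, and nothing elsewhere supplies a method that could measure agreement.

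Second, McNemar is an assumption, as are the single binary response, the 20% rate and the 30% discordance. Equal discordance is also that test's null hypothesis, so its low rejection rate is simply its size. This is fair, and it is also the point: the null hypothesis of such a test is compatible with almost any level of agreement. Step 4 shows that the result does not depend on the choice of test.

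Third, a reader might infer that no significant difference would always be found at chance-level agreement. That is too strong. It needs similar overall response distributions; Steps 3 and 5 show that a clear shift is often detected. Systematic bias is a reasonable target of the comparison, so the net shift belongs in the report alongside agreement.

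Fourth, a reader might infer that the primary PFS analysis is in doubt because it uses site reads. The documents do not support this: Section 6.2.1 confines the central reads to exploratory work, and objective 2.4.2 does not compare PFS.

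**Conclusion.** The point holds in a limited form. The comparison has no margin and no agreement measure, and a non-significant difference would not show that site and central reads agree. Under the illustrative assumptions (exact McNemar, one binary response per patient, n = 129, 20% response by each reader, 30% symmetric discordance, kappa 0.06), it would be non-significant in about 97% of trials at two-sided 5% and about 92% at one-sided 10%. These figures depend on the two readers having similar response totals. The consequence is confined to an exploratory aim: the primary PFS result is unchanged, but a claim that site reads match central review would have no support.

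**What to change.** Restate the aim in Sections 1.7 and 2.4.2 as estimation of agreement, and add a short paragraph to Section 9.3:

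- For best overall response and for time-point response, report the site-by-central table, percent agreement and (weighted) kappa, with two-sided 80% confidence intervals to match the rest of Section 9.3.
- Report the net shift in category totals, so that systematic bias is visible separately from scatter.
- Report limits of agreement for sums of diameters where both reads record them.
- Define the paired reads: which patients, which of the first three follow-up time points, and what happens when one read is missing. Best response should be derived over the same time points for both readers.
- Allow for several time points per patient, for example with a patient-level bootstrap.
- If equivalence is to be claimed, prespecify a minimum level of agreement.

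The cost is wording and a standard agreement table from data already being collected. The responses to CTEP's comments at the front of the document say that further design changes were not being made because of slow accrual. This is a change of analysis and reporting, not of design, and it remains useful with fewer patients: Step 6 gives an 80% half-width for kappa of about 0.10 to 0.12 at N = 50.
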